### **5.6.1 Required Termination**

Subjects must be withdrawn if participation is determined to be harmful to them, in the opinion of the Protocol PI, CTP Site Coordinator, Lead Investigators, IRB, or CTN DSMB. The possibility of abusive partner behavior and/or a marked increase in emotional distress are the foreseeable adverse effects of participation. Recognition of and intervention for this possible problem is discussed in sections 8.5 and 9.1.3. It is anticipated that subject discontinuation due to perceived intervention detriment will be rare.

### **5.6.2 Consideration of Early Termination**

The Lead Investigators, the Protocol PI, CTP Site Coordinator, IRB, or CTN DSMB may decide to discontinue a subject's participation, if it poses a significant risk to her well-being. The possibility of abusive partner behavior and/or a marked increase in emotional distress are the foreseeable adverse effects of participation.

### **5.6.3 Procedures for Discontinuation**

A subject choosing to withdraw from study, of her own accord, will inform the staff, and be withdrawn, as requested. Such subjects will not be contacted to obtain follow-up assessments.

A subject who is judged, by clinical or research staff, to be placing herself at serious risk for harm by continued study participation will be asked to meet with the CTP Site coordinator and the subject's therapist(s) jointly. The subject, CTP study site coordinator and the subject's therapist(s) will discuss the pros and cons of participation. If the subject chooses to continue, while the coordinator continues to view intervention participation as detrimental, the subject will be withdrawn from intervention but retained in follow-up assessment. As discussed in sections 8.5 and 9.1.3, subjects who are being discontinued will receive crisis intervention from the CTP Site Coordinator and referral for ongoing abuse-protective services, psychiatric treatment and/or other services as needed.

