### **5.6 Subject Discontinuation Criteria**

Subjects are free to withdraw at any time from the study without consequence to their drug abuse treatment in their CTP. During the treatment phase of the study, a patient may be discontinued from the study for a variety of reasons. These include: a serious adverse experience which places her at risk if study participation is continued; serious concurrent illness; or non-compliance with clinic policy or study protocol. Although we anticipate it will be a rare event, a potential problem would arise if a participant drops out of substance abuse treatment (or is discharged from treatment), but wishes to continue attending the protocol intervention to which she is assigned. Since the intent of the

study is to evaluate the interventions conducted within treatment programs these individuals will not be allowed to attend intervention sessions, but will be followed to complete follow up assessments. In addition these individuals will be referred to community resources for HIV prevention information if so desired.

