## **5.7 Replacement of Subjects**

Subjects who withdraw from study after notification of randomization will not be replaced and will be included in all statistical analyses according to the intention to treat (ITT) design.

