### **8.3 Baseline and Follow-Up Assessment Battery**

Participants will be paid in cash or vouchers for completion of the baseline and follow-up assessments. Reasonable and non-coercive reimbursement sums will be determined on a site-by-site basis. All randomized participants will be followed throughout the study in order to maximize follow up rates. If possible, participants should be interviewed in person, including participants who might be incarcerated. The protocol specific assessments (not the Common Assessment Battery or ACASI administered SERBAS) within the Baseline and Follow Up Assessment should be audiotaped. The following instruments will be used at baseline and follow-up:

**8.3.1 Composite International Diagnostic Interview (CIDI):** The substance abuse subsections of the Composite International Diagnostic Interview, Version 2.1 (CIDI-2.1), part of the CTN common assessment battery, will be used to determine whether participants meet DSM-IV criteria for substance abuse or dependence. This is administered at the baseline only.

**8.3.2 Addiction Severity Index-Lite:** The ASI, also included in the CTN common assessment battery, is a standardized, multidimensional, semi-structured, comprehensive clinical interview that provides problem severity profiles and treatment planning information in 6 problem domains commonly affected by substance abuse. These problem domains are: alcohol and substance abuse; medical; psychiatric; legal; family/social; and employment/support. Composite scores for each domain are derived mathematically. A revised version of the 1997 ASI Lite 5th Edition, limited to the items used in the composite scores and some demographic information, will be administered by a research staff member. The full ASI-Lite will be administered at the baseline only.

At the 3-month and 6-month assessment, only the drug and alcohol section will be administered.

**8.3.3 Biologic Measures:** Urine and alcohol screens will be done at the Baseline assessment to substantiate self-report data. The urine drug screen will occur onsite and test for 10 illicit substances. A breathalyzer will be used to screen for blood alcohol concentration (BAC).

**8.3.4 Drug Use and Drug Injection Risk Behavior Assessment:** The RBS drug use and injection practice items will be repeated at the 3 and 6 month follow-up visits.

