All study related AEs and SAEs will be followed until resolution. Monitoring and reporting of SAEs will be maintained by the: CTP staff members (e.g. research assistants, therapists, etc.); CTP Site Coordinator; Protocol PI; Study Project Manager; Lead Investigator; and NIDA Medical Monitor.

Figure 3 presents a flow chart for AE and SAE reporting. Only SAEs and related AEs will be recorded and entered into the study database (via the AE CRF). All SAEs will be recorded on the AE CRF, the SAE Form, and a summary narrative provided via the SAE Summary Report. The AE CRF is a form that will be used to document any adverse event that is thought to be serious or study related. The AE CRF is completed at each assessment point and on an as needed basis. If the adverse event is found to be serious, then a SAE Form and SAE Summary Report must be completed. The SAE Form should be completed by or in consultation with the Study Clinician. The SAE Summary Report contains demographic information and an event narrative and should be completed by the Study Clinician.

All SAEs must be reported by fax of the AE CRF, within 24 hours to the Lead Investigator, Protocol PI, Node PI, NIDA Medical Monitor, and to IRBs in accordance with their guidelines. The Study Clinician will be responsible for reviewing the AE CRF and SAE Form, querying the staff as needed, and completing an SAE Summary Report, to be co-signed by the Lead Investigator. Within 14 days, the AE CRF and the SAE Form and the signed SAE Case Summary are forwarded to the NIDA Medical Monitor, Protocol PI, and Node PI. At the same time, reports will be submitted to all involved IRBs per reporting requirements.

All study staff – including research assistants, therapists, CTP Site Coordinator, Protocol PI, Lead Investigator, and Study Project Manager, will receive common training for AE and SAE detection, monitoring and reporting. Training will include: definition of AEs; definition and grading of SAEs; indications and procedures for completing the AE log; indications and procedures for completing AE CRFs; indications and procedures for completing SAE Forms and SAE Summary Reports; and procedures for reporting SAEs.

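### Section 5.6.3 ends outcome follow-up for a woman who withdraws by her own choice, section 8.3 promises follow-up of every randomized woman, and no assessment-only option is stated for a woman who wishes or agrees to stop

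*Protocol*

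**What the plan says.** Section 5.6.3 covers two situations. In the first: "A subject choosing to withdraw from study, of her own accord, will inform the staff, and be withdrawn, as requested". The next sentence sets the consequence: "Such subjects will not be contacted to obtain follow-up assessments". In the second, staff judge participation harmful, meet the woman, and she still wants to go on; then "the subject will be withdrawn from intervention but retained in follow-up assessment".

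Section 5.6 adds a third situation. Women who leave or are discharged from drug treatment but want to keep attending "will not be allowed to attend intervention sessions, but will be followed to complete follow up assessments".

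Sections 5.6.1 (required termination) and 5.6.2 (considered termination) provide for ending participation but do not say whether assessments go on afterwards.

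Section 8.3 gives the general rule: "All randomized participants will be followed throughout the study in order to maximize follow up rates". Section 5.7 says that women who withdraw after notification of randomization are not replaced and "will be included in all statistical analyses according to the intention to treat (ITT) design". Section 11.5.6 defines the primary analysis sample as all randomized subjects.

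Table 2 lists two forms, Study Termination – Treatment (immediate post-intervention visit) and Study Termination – Follow Up (6-month visit).

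**The concern.** The primary outcome is self-reported at 3 and 6 months, so it exists only if the woman is contacted. Whether she is contacted depends on which sentence a site applies, and 5.6.3 and 8.3 give opposite answers for the same woman.

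There is also a gap. No text tells staff to ask a woman who wants to stop whether she means the group sessions or all contact. A remark that she no longer wants to come to the groups can be recorded as study withdrawal, and her outcomes are then not sought although she might have given them.

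This loss need not be equal between arms. The skills arm (SSB) has five sessions of about 90 minutes and the education arm (HE) one of about 60 minutes (6.1), so there is more to stop in SSB. Section 8.5 names introducing condoms, negotiating safer sex and refusing unprotected sex among possible triggers of partner abuse or distress, and SSB sessions 3 and 4 rehearse condom and negotiation skills (6.1.2). Section 8.4.7 says abuse is associated with sexual risk behavior. Differential loss related to risk is therefore plausible, but the protocol does not state it and gives no rate.

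**Working it through.** **1. The rules side by side**

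| Situation | Section | Assessments after sessions stop |
|---|---|---|
| Leaves or is discharged from drug treatment | 5.6 | Kept |
| Wants to continue, coordinator sees detriment | 5.6.3 | Kept |
| Withdraws from the study of her own accord | 5.6.3 | Not sought |
| Wants to stop sessions only | Not addressed | Only the general rule in 8.3 |
| Agrees with staff to stop | Not addressed | Only the general rule in 8.3 |
| Withdrawn under 5.6.1 or 5.6.2 | Not stated | Only the general rule in 8.3 |
| Any randomized woman | 8.3 | Kept, no exception |

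Row 3 contradicts row 7. Rows 4 to 6 are the gap.

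**2. What reaches the analysis.** Model (1) in 11.6.1 has the 3- and 6-month counts as outcomes and the baseline count and monogamy status as covariates. A woman who withdraws before 3 months contributes no outcome. Section 11.5.7 says that women with baseline data only need imputed follow-up values. Under the no-contact rule, 5.7 can be met for them only by imputation.

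**3. Size of a possible bias.** The protocol gives no inputs, so everything here is assumed. Let a share w of an arm withdraw and let withdrawers average g occasions more than completers, with the same g in both arms. The arm's true mean is completer mean + w × g, so the completer mean is too low by w × g. The HE-minus-SSB difference among completers is therefore shifted by

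(w_SSB − w_HE) × g.

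- Equal rates: 0 for any g.
- 10% v 5%: 0.05 × 2 = 0.10 to 0.05 × 17 = 0.85 occasions.
- 20% v 5%: 0.15 × 2 = 0.30 to 0.15 × 17 = 2.55 occasions.
- If g is negative, the shift has the opposite sign and hides benefit.

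The planned differences in 11.2 are 1, 1.5 and 2 occasions. The figures describe an unadjusted comparison of completers, not the planned analysis.

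**4. Effect on power.** No stated figure depends on the withdrawal rule, but 11.2 shows no allowance for loss. First the plan's own figure: Table 1 of 11.2, correlations 0.40/0.10/0.05, 17 v 16, no over-dispersion, stated power 0.85. For an arm in a site with groups of m = 4, n = 20 women and two follow-up measures:

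- Variance of the arm mean = V/(2n) × [1 + ρ1 + 2(m−1)ρ2 + 2(n−m)ρ3] = V/40 × [1 + 0.4 + 0.6 + 1.6] = 0.09V.
- Both arms, V = 17 and 16: 0.09 × 33 = 2.97.
- Less the shared site covariance, 2 × 0.05 × √(17 × 16) = 1.649: 1.321.
- Over 12 sites: 1.321/12 = 0.110, SE = 0.332.
- Power = Φ(1/0.332 − 1.96) = 0.854, which matches 0.85.

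With assumed total loss from all causes of 5, 10, 15, 20 and 30%, this cell becomes 0.841, 0.825, 0.809, 0.790 and 0.746. The 17 v 15.5 contrast in the same row stays at 0.977 or more. In the least favourable row of Table 2 (0.80/0.15/0.05, over-dispersed), that contrast goes from 0.822 with no loss to 0.812, 0.802, 0.790, 0.777 and 0.746. Self-withdrawal would be only part of any such loss.

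**The case against.** The strongest defence is that 5.6.3 concerns withdrawal from the study, where no further contact is a usual consequence and respects the woman's freedom to leave. No text says that a woman who merely misses or gives up sessions loses follow-up; 8.3 covers her by default, and Table 2 already separates ending treatment from ending follow-up. This largely stands. What remains is that 8.3 carries no exception, and that nothing requires staff to establish which kind of stopping she means.

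Four stronger readings are tempting and go beyond the documents:

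- *A woman who accepts advice to stop is lost while one who resists it is kept.* Section 5.6.3 is silent on the woman who agrees after the joint meeting. Treating her as leaving of her own accord is an inference.
- *Section 5.7 cannot be honoured.* It can, because 11.5.7 provides imputation for women with baseline data only.
- *The rule defeats safety follow-up.* Section 9.1.2 says "All study related AEs and SAEs will be followed until resolution", but 5.6.3 bars contact only for obtaining assessments. What is lost is narrower: research assistants elicit adverse events at assessments, so later events would not be picked up by that route.
- *Loss depends on tolerance of the five-session arm and biases the result by a known amount.* The rule is the same in both arms, sessions are paid, and non-attendance does not require withdrawal. No rates are given.

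The analysis also has real protection. Model (1) adjusts for the baseline value of the same count, which should absorb much of a stable difference between withdrawers and completers. Section 11.5.7 plans multiple imputation and two approaches to departures from missing at random. But the same section calls that assumption untestable, and sensitivity analysis shows the consequences of missing outcomes without supplying them.

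**Conclusion.** The contradiction between 5.6.3 and 8.3 is certain from the text, and so is the absence of a stated assessment-only option for a woman who wishes or agrees to stop. Some obtainable primary outcomes may be lost as a result.

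The size and direction of any bias are unknown. Bias in the unadjusted completer comparison is zero if withdrawal rates and withdrawer–completer gaps are equal across arms. Under the assumed rates and gaps above it ranges from 0.10 to 2.55 occasions, before baseline adjustment, imputation or sensitivity analysis. Those figures show what would have to be true for the loss to matter; they are not estimates for this trial. For power, the 0.85 cell falls just below 80% at about 20% total loss, again an assumed figure.

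This is a worthwhile and inexpensive improvement. The evidence does not make it a correction without which the trial fails.

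**What to change.** Reconcile sections 5.6 to 5.7 with 8.3 by using two defined terms throughout:

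- **Stopping intervention sessions**, whoever decides. The woman is asked to keep the 3- and 6-month assessments and stays on the contact list.
- **Withdrawing consent for further contact**, stated explicitly by the woman and recorded on the existing Study Termination – Follow Up form. Only this ends contact for assessments.

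Name the second as the exception in 8.3. State in 5.6.1 and 5.6.2 which term applies, and have staff ask which one a woman means before contact ends. When sessions should be stopped is left to the sponsor.

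The cost is minor protocol and consent wording plus a few extra paid interviews; both termination forms already exist. The change works only if it is in place before women withdraw, because a missed 3-month assessment cannot be recovered later.

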## **5.7 Replacement of Subjects**

Subjects who withdraw from study after notification of randomization will not be replaced and will be included in all statistical analyses according to the intention to treat (ITT) design.

## **6.0 Study Treatments**

### **6.1 Study Therapies**

There are two intervention conditions in the proposed study: 1) five-session SSB group; and 2) a single standard-of-care HIV education session, serving as a comparison condition. Both interventions will be carried out by CTP female drug treatment counselors who receive approximately 20 hours of training. In [name]'s and Schilling's

studies, skills building intervention training required 20 hours. Both interventions are manual-driven. These two features will make ongoing technology transfer to the CTPs highly likely. The HE condition consists of one approximately 60-minute session, while the SSB will consist of 5 approximately 90-minute groups. Each condition will consist of 3-8 women. Each intervention condition will be run by two female co-leaders.

### **6.1.1 HIV Education (HE)**

This intervention will consist of the HIV information covered in the first session of the SSB intervention using discussion, flip chart visual materials and informational and resource handouts. This will be an approximately 60 minute group session covering: HIV definitions, transmission, testing and counseling, treatment, and prevention. Certificates will be distributed at the end of the session. Participants will be paid for their attendance to the treatment groups. Reasonable and non-coercive reimbursement sums will be determined on a site-by-site basis. Women will be paid in cash or vouchers (as determined by the CTP) for their participation. It is recommended that participants are paid only if they attend the majority of the session (40 minutes), although the decision to do this may vary based on local IRBs. Paying participants to attend treatment sessions calls into question the issue of sustainability. In the CTPs, patients are not paid to attend sessions. The current protocol is voluntary research. It is the investigators' experience that it is difficult to attract a wide distribution of patients at voluntary sessions without monetary incentives. If the SSB intervention proves efficacious, then CTPs could make it a mandated part of treatment and, thus, eliminate the need for incentives.

### **6.1.2 Safer Sexual Skills Building (SSB)**

This intervention will consist of 5 approximately 90-minute group sessions. Participants will be paid for their attendance to the treatment groups in cash or vouchers. Reasonable and non-coercive reimbursement sums will be determined on a site-by-site basis. It is recommended that participants are paid only if they attend the majority of the session (60 minutes), although the decision to do this may vary based on local IRBs.

Primarily through active problem-solving, behavioral modeling, role play rehearsal, interval practice, troubleshooting, and peer feedback and support, this intervention will build cognitive, affective and behavioral skills for safer sexual decision making and behavior. The 5 sessions entail:

- 1)** Using discussion, flipchart visual materials, and informational and resource handout materials, the counselor will conduct a 90 minute session covering: HIV/STD definitions, transmission, testing and counseling, treatment, and prevention.
- 2)** Using discussion, flipchart visual materials, risk vignettes, and risk assessment worksheets, women will assess their own personal risk for HIV/STDs. Using discussion, flipchart visual materials, HIV sexual risk behavior and alcohol and drug use vignettes and triggers assessment worksheets, women will identify the internal and external triggers to HIV sexual risk behavior. Particular emphasis will be placed on the role of (1) partner pressure, threat and abuse; and (2) alcohol and drug use effects. Women will also identify sources of support for safer sexual behavior and ways of seeking their help.
- 3)** Using discussion, flipchart visual materials, and male and female genital models, women will: a) observe male and female condom handling, insertion and removal; b) rehearse these skills; and c) give feedback about these methods. Women will use the SODAS (stop; options; decide; action; self-praise) problem-solving model to brainstorm constructive responses to HIV sexual risk and drug use vignettes. Women will identify

adverse effects posed by safer sexual behavior and negotiation for them. Particular emphasis will be placed on risk of partner violence, sexual abuse and verbal abuse, relationship break-up, and relationship strain.

**4)** Using safer sexual behavior and safer sexual negotiation vignettes women will: a) observe behavioral modeling of a range of action options including planned passivity, cajoling, assertiveness, frank withdrawal and other options; b) brainstorm pros and cons of these options; c) problem-solve courses of action for these options; and d) rehearse these skills in role plays. Women will identify adverse effects posed by safer sexual behavior and negotiation for them. Particular emphasis will be placed on risk of partner violence, sexual abuse and verbal abuse, relationship break-up, and relationship strain.

**5)** Using flipchart visual materials and “take home message” worksheets, women will wrap up and summarize the major action options they have identified during the intervention. Through the use of unsafe sexual behavior vignettes, women will become familiar with cognitive-behavioral techniques for “breaking” drug and alcohol use and/or unsafe sexual behavior slips before they become full-blown relapses. Resource handouts, especially for dealing with partner violence, seeking HIV/STD testing and counseling, and seeking women’s activism organizations will be reviewed. A graduation ceremony will be held, and certificates will be given.

## **6.2 Selection and Training of Therapists**

Therapists will be recruited from the counseling staff of the CTP sites to deliver both study interventions. Priority will be given to counselors with group therapy and/or HIV education experience. Two therapists will be trained in each site. If there are less than two interested and available counselors, the CTP Study Coordinator will recruit therapists from the community. As described in section 6.3.3, procedures for training and administration of both study interventions will maximize adherence to each therapy, respectively. Using the intervention manuals, the therapists will receive 20 hours of training. Training will also include self-observation and self-restraint in limiting discussion of SSB intervention material strictly to the intervention sessions for which it is intended. HIV safer skills building group intervention training will be conducted by the Lead Investigator and a member of the intervention author’s ([name].) team. Training for therapists unable to attend the Lead Investigator training will be conducted at each local site in consultation with the Lead Node.

We acknowledge the possible advantage, to protect the discreteness of each condition, of using distinct facilitators. Nevertheless, we judge the advantages of using same facilitators to outweigh those. We propose that, in using same facilitators, we: (1) reduce the possibility of confounding intervention with facilitator effect; (2) deliver training in two interventions rather than one, to CTP facilitators; and (3) increase the range of CTPs who could participate –particularly small-staff programs.

